### **6.10.1 Completed Subject**

A completed subject is defined as one who completes all days of planned participation through completion of the Day 8 procedures.

### **6.10.2 Non-completing Subject**

A non-completing subject is defined as one who exits the study by their own volition or at the discretion of the Investigator and/or the Sponsor Safety Officer. Any subject may decide to voluntarily withdraw from the study at any time without prejudice. In the event that discontinuation of treatment is necessary, the Investigator will make every attempt to complete all subsequent safety assessments.

### **6.10.3 Subject Discontinuation**

The subject may discontinue from the study for the following reasons (to be recorded on the CRF):

- Adverse Events (AEs including, in the opinion of the investigator, clinically relevant abnormalities and intercurrent diseases reported by the subject or observed by the investigator with documentation on the CRF).
- Administrative: This category is for reasons unrelated to the investigational product including:
  - Non-compliance (e.g., use of prohibited concomitant medication and/or failure to attend scheduled follow-up visits)
  - Other

All subjects who discontinue Investigational Product due to a report of an AE must be followed-up and provided appropriate medical care until their signs and symptoms have remitted or stabilized or until abnormal laboratory findings have returned to acceptable or pre-study limits.

### **6.10.4 Entire Study Terminated**

The entire study may be discontinued by the Investigator or the Sponsor. Prompt, written notice of reasonable cause to the other party (Sponsor or Investigator, respectively) is required. Prompt notice to the IRB and to regulatory authorities is also required.

### **6.10.5 Completed Study**

The study is completed when the planned enrollment has been completed, and all the enrolled subjects have completed the study.

## **6.11 Appropriateness of Measurements**

The ophthalmic and systemic measures used in this study are consistent with standard of care.

## 7. STUDY ACTIVITIES

A detailed Schedule of Visits and Procedures is provided in [Appendix 1](#). Details of procedures to be performed are provided in [Appendix 2](#).

### 7.1 Screening Visit (Visit 1)

This visit may take place at any time of the day.

Subjects with a diagnosis of POAG or OHT in both eyes (POAG in one eye and OHT in the fellow eye is acceptable) are eligible to be screened for this study. Individuals who are potential subjects will arrive at the Investigator's office. A member of the Investigator's staff will interview the individual as to their qualifications for participation in the study. Individuals will be asked to review the informed consent, discuss issues as needed, and to sign the form. A medical and ophthalmic history including systemic and ocular medication use will be taken, and demographic measures recorded. An examination will be conducted, including measurement of heart rate and blood pressure, and an ophthalmic examination (to include ocular symptoms, visual acuity (VA), central corneal thickness by ultrasound pachymetry, IOP, biomicroscopy, gonioscopy, and identification of episcleral vein (utilizing a slit lamp) that will be used for EVP measurement [REDACTED]). If no exclusion criteria are identified, dilated ophthalmoscopy will be performed. Subject symptoms will be queried. The investigator will evaluate the results of these examinations for possible enrollment of the individual into the study.

Subjects may be treatment-naïve or taking a prescribed IOP-lowering medication at the time of Screening. If the subject is currently taking an ocular hypotensive medication, once they have agreed to participate in the study and have signed informed consent, they will agree to washout from their current medication and refrain from taking it until they have exited the study. Washout from current ocular hypotensive medication will be conducted according to the times noted in [Table 1](#), and depends on the type of IOP-lowering treatment.

Evaluation of eyedrop instillation performance: Subjects will be provided a bottle of commercially available, multi-dose, non-medicated artificial tears in a room with access to water and soap. They will be asked to instill a drop of the artificial tear in each eye under the observation of a member of the investigator's staff. The staff will observe the subject to assure that the subject instills one drop (and one drop only) of the artificial tear into each eye, without touching the tip of the bottle to their eye or face ([Stone 2009](#)). The staff member may work with the individual to improve their delivery technique to meet this standard. If the subject cannot demonstrate proper delivery of the eye drop, or if staff member feels that the individual will be unable to do so consistently, then the subject will be excluded from further study participation.

All females of childbearing potential must have a negative pregnancy test result at the screening examination and must not intend to become pregnant during the study.

## 7.2 Treatment Period

### 7.2.1 Visit 2 (Day 1, Qualification/Baseline) Procedures

This visit should occur no more than 2 to 7 days following the Screening visit, if the subject is treatment-naïve, or following the appropriate washout time prescribed for the IOP-lowering medication(s) they were taking at screening ([Table 1](#)).

Individuals who do NOT meet the IOP requirements at any of the timepoints in this visit may return for up to 2 additional visits within 1 week of failing this visit. Individuals returning for an unscheduled visit within 1 week to re-attempt IOP qualification are required to ONLY re-measure IOP in both eyes.

Upon return of the requalification visit, such individuals' IOP measurements would need to qualify at all timepoints (08:00, 13:00, and 16:00)

Individuals who screen fail due to IOP being  $\geq 30$  mmHg in either eye (exclusion criterion) MAY NOT return for additional qualification visits.

#### 7.2.1.1 Visit 2 08:00 hours ( $\pm 30$ min)

Vital signs will be collected (heart rate and blood pressure), and the subject's general well-being and ocular symptoms will be collected (including medical history, concomitant medications and any adverse events). An ocular examination will then take place, including VA, IOP, and biomicroscopy.

Please note that the episcleral vein may be assessed during this visit timepoint if it was not able to be assessed during the Screening visit.

IOP should be  $>20$  mmHg and  $<30$  mmHg in both eyes in order for the subject to continue to be eligible for qualification and enrollment into the study. Furthermore, the IOP should not differ by more than 4 mmHg between the eyes. Subjects will be re-examined at 13:00 hours. Note; subjects are free to leave the site between visits, provided they agree to not participate in strenuous activities or consume alcohol, and return promptly for the next visit.

#### 7.2.1.2 Visit 2 13:00 hours ( $\pm 30$ min)

The following procedures will be conducted:

- IOP, which must be  $>17$  mmHg but  $<30$  mmHg in order for the subject to be considered eligible to proceed with the Qualification visit.
- EVP (see [Appendix 2](#) for procedures).
- Trabecular (tonographic) outflow facility (see [Appendix 2](#) for procedures).

The subject will then return for their final Qualification examination at 16:00 hours. Note; subjects are free to leave the site between visits, provided they agree to not participate in strenuous activities or consume alcohol, and return promptly for the next visit

#### 7.2.1.3 Visit 2 16:00 hours ( $\pm$ 30 min)

The following procedures will be conducted:

- IOP, which must be  $>17$  mmHg but  $<30$  mmHg in order for the subject to be considered eligible to proceed in the study.
- EVP (see [Appendix 2](#) for procedures)
- Trabecular (tonographic) outflow facility (see [Appendix 2](#) for procedures)

Provided the Investigator is satisfied that the subject meets all of the Inclusion criteria and none of the Exclusion criteria, and the subject continues to be willing to participate in the study, then the subject will be enrolled and randomized to a treatment schedule. After obtaining randomization information, the appropriate subject kit will be provided to the subject.

The subject will be instructed to begin dosing the following day (Day 2) between 08:00 and 10:00 hours, and to dose every day for 6 days at the same time (between 08:00 and 10:00 hours). One drop from the bottle labelled “Right Eye” should be dispensed into the right eye every day, and one drop from the bottle labelled “Left Eye” into the fellow eye once every day. Subjects will return to the site 7 days later (Day 8) BEFORE taking their study medication for their exit visit procedures.

#### 7.2.2 Visit 3 (Day 8, Exit)

This visit should occur 7 days after Visit 2 (qualification/baseline visit), and the subject should be instructed to bring all medications with them to the site. The subject should not take their study medication before arriving at the site, but should be instructed that they will administer their medication at the site following their 08:00 hour assessments have been performed.

##### 7.2.2.1 Visit 3 08:00 hour ( $\pm$ 30 min)

Subjects will be asked how they have been feeling since their last visit, and to describe any TEAEs they may have experienced.

The following procedures will be performed:

- Heart rate and blood pressure
- Ocular symptoms
- Visual Acuity

- Biomicroscopy
- IOP

Site personnel will then instill their final doses of study medication and all medication, used and unused, will be collected from the subject. The subject will then be asked to return for their next assessments at 13:00 hours. Note; subjects are free to leave the site between visits, provided they agree to not participate in strenuous activities or consume alcohol, and return promptly for the next visit.

#### 7.2.2.2 Visit 3 13:00 hours ( $\pm$ 30 min)

The following procedures will be conducted:

- IOP
- EVP (see [Appendix 2](#) for procedures).
- Trabecular (tonographic) outflow facility (see [Appendix 2](#) for procedures).

The subject will then return for their final examination at 16:00 hours. Note; subjects are free to leave the site between visits, provided they agree to not participate in strenuous activities or consume alcohol, and return promptly for the next visit

#### 7.2.2.3 Visit 3 16:00 hours ( $\pm$ 30 min)

The following procedures will be conducted:

- IOP
- EVP (see [Appendix 2](#) for procedures).
- Trabecular (tonographic) outflow facility (see [Appendix 2](#) for procedures).

The subject will then be thanked for their participation in the study, and will be dismissed.

### 7.3 **Unscheduled Visit**

An unscheduled visit is any visit to the Investigator other than the specific visits requested in the protocol, as may be possibly required for the subject's ophthalmic condition. The Investigator will perform all procedures necessary to evaluate the study participant at these visits and record any TEAEs in the eCRF. If the unscheduled visit occurs prior to Day 8, and the subject is to discontinue from the study for any reason, every effort should be made by the site to conduct the assessments and procedures outlined above ([Section 7.2.1.3](#)) for the Exit visit.

## **8. QUALITY CONTROL AND ASSURANCE**

The progress of the study will be monitored by on-site, written, and telephone communications between personnel at the Investigator's site and the Study Monitor. The Investigator will allow the Sponsor or designee to inspect all documents pertinent to the study, including (but not limited to):

- CRFs
- Subject records (source documents)
- Signed consent forms
- Records of study medication receipt, storage, preparation, and disposition
- Regulatory files related to this study

## **9. PLANNED STATISTICAL METHODS**

### **9.1 General Considerations**

All statistical analyses will be performed by the Sponsor designee using SAS® software. A separate Statistical Analysis Plan will be produced that will provide complete details regarding the data handling and analysis methods.

Continuous summary statistics (sample size, mean, SD, median, minimum, and maximum) will be presented by treatment for each time point (and for the diurnal mean) at each visit and for the change from baseline and percent change from baseline. All study data will be listed by treatment, subject, and time point (as applicable).

For measurements of AHD, baseline will refer to the time-relevant measure at Visit 2, Day 1 (e.g., IOP at 13:00 hours at Visit 2 will be the baseline for IOP at 13:00 hours at Visit 3). For all other variables, baseline is defined as the last measurement prior to the first dose of study medication.

All statistical tests will use one-sided significance level of 5%. Where applicable, 2-sided 90% (equivalent to one-sided 90% confidence intervals [CIs]) and 95% CIs will be reported

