## 1.2 Investigational Product and Prior Experience

Netarsudil mesylate (AR-13324) is the active compound in netarsudil ophthalmic solution 0.02%. It is a novel Rho-kinase and norepinephrine transporter inhibitor developed by Aerie Pharmaceuticals, Inc. for reducing elevated IOP in patients with open-angle glaucoma (OAG) and/or ocular hypertension (OHT), and formulated to be dosed by topical instillation to the eye, 1 drop, once daily. Based on the results of non-clinical (Wang 2015, Kiel 2015) and early clinical (AR-13324-CS102) studies, netarsudil appears to have multiple mechanisms of action for lowering IOP, including increasing trabecular outflow facility and reducing EVP. Netarsudil has also been shown to decrease the production of aqueous humor in monkeys (Wang 2015), [REDACTED]

Aerie has completed a total of 8 clinical studies evaluating the dose response and dose frequency response of netarsudil ophthalmic solutions, as well as their ocular and systemic safety, including 3 well-controlled Phase 3 studies. In all Phase 3 studies, the efficacy of netarsudil ophthalmic solution 0.02% QD was non-inferior to timolol maleate ophthalmic solution 0.5% dosed twice daily (BID) in the Per Protocol (PP) and Intent To Treat (ITT) populations of subjects with maximum baseline IOP <25 mmHg, and <27 mmHg. Additionally, a favorable safety profile was demonstrated for netarsudil ophthalmic solution 0.02% QD through the duration of both studies. The majority of adverse events (AEs) were ocular and of mild or moderate intensity. [REDACTED]

A phase 1 study, AR-13324-CS102, evaluated the AHD of netarsudil in a population of healthy volunteers. The study demonstrated a mean reduction in IOP compared to baseline of 4.6 mmHg (~27%). Additionally, netarsudil demonstrated the following effects on AHD:

- Increase in outflow facility (~20% relative to baseline,  $p < 0.05$ )
- Decrease in EVP (~10% relative to baseline,  $p < 0.05$ )
- Decrease in aqueous flow (~15% relative to baseline,  $p < 0.08$ )
- Increase in uveoscleral outflow (calculated, not statistically significant relative to baseline)

The present study will evaluate the effect of netarsudil on AHD in subjects with POAG or OHT. Since trabecular outflow facility is of key clinical relevance and potentially a mechanism of action of netarsudil, this study will be powered with outflow facility as the primary efficacy parameter. IOP and EVP will also be evaluated.

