### **9.4.3 Efficacy Analysis**

The primary endpoint is the mean change from baseline in the mean diurnal trabecular outflow facility on Day 8. The null and alternative hypotheses, based on the primary variable are as follows:

H01: The difference between study eyes treated with Netarsudil Ophthalmic Solution 0.02% and study eyes treated with Placebo, in the mean change from baseline of mean diurnal trabecular outflow facility = 0 on Day 8.

H11: The difference between study eyes treated with Netarsudil Ophthalmic Solution 0.02% and study eyes treated with Placebo, in the mean change from baseline of mean diurnal trabecular outflow facility > 0 on Day 8.

The null hypothesis will be tested using a paired t-test with  $\alpha=0.05$ . One-sided p-values, two-sided 90% CIs, and two-sided 95% CIs will be presented.

Secondary AHD measures: IOP and EVP will be analyzed similarly to the primary endpoint.

Similar to the primary efficacy analysis, mean differences in diurnal means of AHD measures and mean differences at the individual time points will be tested with paired t-tests. One-sided p-values, two-sided 90% CIs, and two-sided 95% CIs will be presented. Means within each treatment comparing diurnal mean on Day 8 with baseline diurnal mean and comparing individual time points on Day 8 with the corresponding time points at baseline visit will also be tested using paired t-tests. The same inferential statistics will be presented for these.

Mean percent change from baseline in diurnal means of AHD measures and mean percent change from baseline in AHD measures at individual timepoints will be tested using paired t-tests. The same inferential statistics as for the primary endpoint will be presented for these.

All AHD measures will be summarized by treatment and visit/time point using descriptive statistics (n, mean, median, standard deviation, minimum, and maximum).

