8.4 Data Analysis Conventions

All data analysis will be performed by . Statistical programming and analyses will be performed using SAS® Version 9.4 or higher. Output will be provided in rich text format (RTF) for tables and portable document format (PDF) for tables, listings, and figures using landscape orientation. All study data will be listed by subject, treatment, visit, and time point (as applicable) based on all randomized subjects unless otherwise specified.

All continuous study assessments will be summarized by treatment and visit (as applicable) using descriptive statistics (number of observations [n], mean, median, standard deviation, minimum, and maximum). All categorical study assessments will be summarized by treatment, visit, and time point(as applicable) using frequency counts and percentages.

All study data entered in the database will be listed by subject, visit, and time point (as applicable).

All statistical tests will be performed with a significance level of 5% (one-tailed). Where applicable, two-sided 90% and 95% CIs will be reported.

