13.1 Primary Analysis

The primary efficacy endpoint is the mean change from baseline in mean diurnal trabecular outflow facility (average of 13:00 and 16:00 hour measurements) per treatment on Day 8. Baseline mean diurnal outflow facility is defined as the average of 13:00 and 16:00 hour measurements on Day 1, Visit 2.

The null and alternative hypotheses, based on the primary endpoint, are as follow:

H01: The difference between study eyes treated with Netarsudil Ophthalmic Solution 0.02% and study eyes treated with Placebo, in the mean change from baseline of mean diurnal trabecular outflow facility = 0 on Day 8.

H11: The difference between study eyes treated with Netarsudil Ophthalmic Solution 0.02% and study eyes treated with Placebo, in the mean change from baseline of mean diurnal trabecular outflow facility > 0 on Day 8.

The null hypothesis will be tested using a paired t-test with alpha=0.05. One-sided p-values, two-sided 90% confidence intervals (CI), and two-sided 95% CIs will be presented. The trabecular outflow facility will be summarized by treatment and visit/time point using continuous descriptive statistics (and listed by subject.

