13.2 Secondary Analyses

The secondary efficacy endpoints include:

- Mean change from baseline in mean diurnal IOP (average of 13:00, and 16:00 hour measurements) and mean diurnal EVP (average of 13:00 and 16:00 hour measurements) per treatment on Day 8
- Mean diurnal values for all AHD (trabecular outflow facility, IOP, EVP) per treatment on Day 8
- Mean values for all AHD at the individual 13:00 and 16:00 hourtime points per treatment on Day 8
- Mean change from baseline for all AHD at the individual 13:00 and 16:00 hour time points per treatment on Day 8. Baseline individual time points are defined as the corresponding measurements on Day 1, Visit 2
- Percent (%) change from baseline in diurnal means for all AHD per treatment on Day 8
- Percent (%) change from baeline at the individual 13:00 and 16:00 time points for all AHD per treatment on Day

Mean change from baseline in mean diurnal IOP and EVP will be analyzed similarly to the primary endpoint.

Similar to the primary efficacy analysis, mean differences in diurnal means of AHD measures and mean differences at the individual time points will be tested with paired t-tests. One-sided p-values, two-sided 90% CIs, and two-sided 95% CIs will be presented. Means within each treatment comparing diurnal mean on Day 8 with baseline diurnal mean and comparing individual time points on Day 8 with the corresponding time points at baseline visit will also be tested using paired t-tests. The same inferential statistics will be presented for these.

Mean percent change from baseline in diurnal means of AHD measures and mean percent change from baseline in AHD measures at individual timepoints will be tested using paired t-tests. The same inferential statistics will be presented for these.

All secondary efficacy endpoints will be summarized by treatment and visit/time point using continuous descriptive statistics.

14. Exploratory Analyses

Not applicable.

15. Safety Analyses

All safety analyses will be conducted using the Safety population.

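### Do the mislabelled 90% interval in Protocol 9.1 and the unwritten direction for IOP and EVP undermine the one-sided tests?

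*Protocol*

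**What the plan says.** Protocol 9.1 applies a one-sided 5% level to every test and adds: "Where applicable, 2-sided 90% (equivalent to one-sided 90% confidence intervals [CIs]) and 95% CIs will be reported". SAP 8.4 keeps the 5% one-tailed level but says only: "Where applicable, two-sided 90% and 95% CIs will be reported". SAP Section 1 gives the SAP's methods precedence over the protocol's.

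The alternative hypothesis appears in the protocol synopsis, Protocol 9.4.3, SAP 2.4 and SAP 13.1. Each time it concerns the netarsudil-placebo difference "in the mean change from baseline of mean diurnal trabecular outflow facility > 0 on Day 8". Protocol 9.4.3 and SAP 2.4 introduce it as resting on the primary variable.

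For the secondary measures SAP 13.2 states: "Mean change from baseline in mean diurnal IOP and EVP will be analyzed similarly to the primary endpoint". It asks for paired t-tests, one-sided p-values and two-sided 90% and 95% intervals. The same statistics apply to individual time points, percent changes and within-treatment changes. No direction is given for any of these.

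**The concern.** There are three grounds for worry.

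- **Confidence level.** A one-sided 90% bound carries a 10% error, twice the 5% level set in the sentence before. If such a bound were reported, interval and test could point different ways.
- **Direction for IOP and EVP.** If the positive alternative is carried over with the rest of the primary method, the p-values test for a rise. Protocol 1.2 reports a Phase 1 fall of 4.6 mmHg in IOP and of about 10% in EVP. A real benefit could then be printed with a p-value near 1.
- **Within-treatment tests.** Placebo eyes also get one-sided p-values, and neither document says which way they are expected to move.

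A one-sided p-value means nothing until its tail is fixed. If the tail were chosen after seeing the data, a nominal 5% test would have a real error rate of 2 × 5% = 10%.

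**Working it through.** **Reproducing the plan's power.** Inputs from Protocol 9.2: SD 0.06 per treatment, between-eye correlation 0.40, difference 0.08, one-sided alpha 0.05, n = 16.

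- SD of the paired difference = √(2 × 0.06² × (1 − 0.40)) = 0.0657, printed in the plan as 0.07.
- With 0.07: SE = 0.07/√16 = 0.0175; noncentrality = 0.08/0.0175 = 4.571; critical t (15 df) = 1.753; power = 99.7%. With 0.0657 it is 99.9%. Both agree with the stated figure of more than 95%.
- 16/(1 − 0.20) = 20 randomized, as stated.

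**The interval.** Margin = t × 0.0175 at 15 df:

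| Interval | t | Margin | Error per tail |
|---|---|---|---|
| Two-sided 90% (= one-sided 95%) | 1.753 | 0.0307 | 5% |
| One-sided 90% (= two-sided 80%) | 1.341 | 0.0235 | 10% |
| Two-sided 95% | 2.131 | 0.0373 | 2.5% |

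The label in Protocol 9.1 belongs to the second row. The synopsis, Protocol 9.4.3 and SAP 8.4, 13.1 and 13.2 ask for the first and third rows. No section plans the second. The interval that will be produced is the one whose limit excludes zero exactly when the one-sided 5% test rejects.

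**The direction.** The documents give no SD or correlation for the IOP difference, so the inputs here are assumptions: correlation 0.4 borrowed from outflow facility, n = 16, and a range of differences and per-eye SDs. SE = SD × √1.2 / 4; t = difference/SE.

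| Difference (mmHg) | SD per eye | SE | t | p, upper tail | p, lower tail | Two-sided 90% CI |
|---|---|---|---|---|---|---|
| −3 | 2.5 | 0.685 | −4.38 | 0.9997 | 0.0003 | −4.20 to −1.80 |
| −3 | 5 | 1.369 | −2.19 | 0.978 | 0.022 | −5.40 to −0.60 |
| −1 | 4 | 1.095 | −0.91 | 0.81 | 0.19 | −2.92 to 0.92 |

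In each row the two p-values sum to 1, and the upper confidence limit lies below zero exactly when the lower-tail p is below 0.05. A p-value from the wrong tail would therefore be visible beside its interval and could be converted by subtraction. EVP is measured at one site in a subset, so its n is unknown and no EVP figure is offered.

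**What the text supports.** The positive alternative is tied by name to outflow facility. The instruction for IOP and EVP refers to the method of analysis: paired t-test, one-sided p-value, two intervals. The direction can be read from Protocol 1.2 (both fell in Phase 1), Protocol 3.2 (the drug lowers IOP and is believed to reduce EVP) and the responder rule in Protocol 9.3.1 (netarsudil-eye IOP at least 2 mmHg below baseline).

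**The case for a change.** The strongest opposing case is that the SAP leaves the direction unwritten and that its Section 17 declares no departures from the protocol's analyses, so the protocol's slip is never acknowledged. A programmer who reuses the primary code would get the upper tail for IOP and EVP. Stating the tail takes a line of text and is worth most before unmasking.

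Part of this stands. The parenthesis is an error, and the direction for the secondary and within-treatment tests is indeed not written down. But the fault in the first is confined to a label. In the second, all the material on IOP and EVP in the protocol points one way, so there is no real freedom to pick a tail after the fact.

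The within-placebo tests have no such anchor. They are supporting, unadjusted comparisons, and each comes with two-sided intervals that depend on no choice of tail. Using two-sided p-values there would be a preference that departs from the plan's uniform one-sided rule. Moving to a one-sided 2.5% level would be affordable (98.9% power at n = 16, SD 0.07), but it corrects no error shown here, and the two-sided 95% interval already lets a reader apply that standard.

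**Conclusion.** No change to the plan follows. The confidence-level statement is a clerical slip in one parenthesis of the protocol, absent from the SAP that governs the analysis; it alters no interval, test, alpha or sample size. The missing direction for IOP and EVP is a detail an analyst would fill as a decrease, from the protocol's own account of the drug.

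The p-values near 1 arise only if the positive alternative is transferred literally to variables it does not name. Their size (0.81 to 0.9997 in the cases shown) rests on assumed IOP inputs. The conclusion relies on the two-sided intervals being reported for every comparison, as both documents require. The primary analysis keeps its 99.7% power at n = 16 under the plan's assumptions.
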